2.2 Aims and Objectives of the Study

Our rationale for examining a genotype-guided approach to acute and chronic pain management is based on the importance of *CYP2D6* for the bioactivation of tramadol, codeine, and hydrocodone and data from a pilot study supporting improved pain control in IM/PMs in the genotype-guided arm who are taking these drugs at baseline. Similarly, the rationale for examining a genotype-guided approach to depression medication therapy is based on the demonstrated role of *CYP2D6* in the bio inactivation and *CYP2C19* oxidation of select, commonly used SSRIs. Secondly, data from industry sponsored trials support the hypothesis of improved symptom control in a genotype-guided arm.

Acute Pain: Determine if a genotype-guided approach to acute post-surgical pain therapy leads to improved pain control compared to usual care, as defined by a decrease in the SIA score. Secondarily, we will evaluate whether this approach leads to reduced use of DEA Schedule II opioids and reduced pain intensity.

Chronic Pain: Determine if a genotype-guided approach to pain therapy in participants with at least 3 months of chronic pain leads to improved pain control compared to usual care.

Depression: Determine if genotype-guided dosing or selection of antidepressants among participants with at least 3 months of depressive symptoms who require new or revised antidepressant therapy leads to improved control of depression, compared to usual care.

3. ENDPOINTS

3.1 Primary Endpoint(s)

Acute pain: The primary endpoint for the acute pain study is the SIA score, a composite of pain and opioid usage, at 10 days post-surgical procedure. See Appendix A for the SIA score rationale.

Chronic pain: The primary endpoint for the chronic pain study is change in composite pain intensity score, assessed using the PROMIS pain intensity survey, from baseline to 3 months post return of genetic testing results to the provider.

Depression: The primary endpoint for the depression study is change in depression score, assessed using the PROMIS Emotional Distress - Depression 8b survey (adults) or PROMIS pediatric depressive symptoms (pediatric), from baseline to 3 months post return of genetic testing results to provider.

3.2 Secondary Endpoints

Secondary endpoints include:

All Trials

1. Overall well-being at 6-month follow-up
2. Sub-domains of overall well-being: pain interference, physical function, sleep disturbance, social role and activities functioning, fatigue, anxiety, and depression at 6-month follow-up
3. Concordance between metabolizer phenotype and prescribed medication

Acute pain

1. Pain intensity at 10 days post-surgery
2. Opioid usage at 10 days post-surgery
3. Prescription pain medication misuse score at 3-months post-surgery
4. Mobility at 1-month post-surgery
5. Opioid persistence 6 months post-surgery

Chronic pain

1. Pain reduction magnitude at 3-month post return of genetic testing results to provider, relative to baseline
2. Proportion of participants achieving clinically significant pain reduction (30% reduction from baseline) at 3-months post return of genetic testing results to provider
3. Prescription pain medication misuse at 3-months post return of genetic testing results to provider

Depression

1. Change in PHQ-8 score between baseline and 3 months
2. Achieve 50% reduction in PHQ-8 scores at 3 months, relative to baseline
3. Medication side effects severity burden at 3 months
4. Participant medication adherence at 3 months
5. Achieve remission at 6 months, defined as PROMIS depression score ≤ 16
6. Achieve remission at 6 months, defined as PHQ-8 score ≤ 4

4. Study Arms & Design

This is a prospective, multicenter, subset analysis of 1:1 randomized Intervention (immediate PGx testing and genotype-guided opioid or SSRI therapy with clinical decision support) vs. Control (usual care with delayed PGx testing) pragmatic, open label clinical trial (Figure 1). The three trials are 1) genotype-guided opioid therapy among post-surgical acute pain participants (Acute Pain, Figure 1A), 2) genotype-guided opioid therapy among chronic pain participants (Chronic Pain, Figure 1B), and 3) genotype-guided SSRI therapy in participants with depression (Depression, Figure 1C). Trial-specific outcomes will be compared between participants in the intervention arm and control arms who have an actionable phenotype. Actionable phenotypes are defined as CYP2D6 IM and PMs (i.e. CYP2D6 activity score ≤ 0.75) for the acute pain and chronic pain trials and CYP2C19 UM, RM and PMs or CYP2D6 UM and PMs for the depression trial.

[figure not shown]

Figure 1. ADOPT PGx Trial Design

Intervention participants are denoted by blue boxes and blue lines, control participants are denoted by orange boxes and orange lines. Return of results are denoted with black outlines, endpoint comparison groups (actionable phenotypes in the control and intervention arms) are denoted with red outlines, and * denote timing of the primary endpoint collection. Time 0 denotes the time from which the follow-up assessment timing begins.

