5. STUDY POPULATION

5.1 Inclusion Criteria

Acute Pain

- Age \geq 8 years
- English speaking or Spanish speaking
- Elective/planned surgery types with planned or anticipated to be treated with tramadol, hydrocodone, or codeine pain management at an enrolling site, which may include orthopedic surgeries(e.g. arthroplasty, spine, etc.), open abdominal surgery, or cardiothoracic surgery and others

Chronic Pain

- Age \geq 18 years
- English speaking or Spanish speaking
- Seen at primary care clinics at an enrolling site (such as, but not limited to, Internal Medicine, Family Medicine, Pediatrics) or seen in pain-relevant specialty clinics
- History of pain for at least the last 3 months
- Currently treated or being considered for treatment with tramadol, hydrocodone, or codeine to improve pain management

Depression

Age \geq 8 years

- English speaking or Spanish speaking
- Patients followed at psychiatry clinics or primary care clinics at an enrolling site (such as, but not limited to, Internal Medicine, Family Medicine, or Pediatrics)
- Documentation of depression and/or provider report of depression
- Evidence of depressive symptoms for at least 3 months based on patient interview or documentation in electronic health records
- Recent initiation of SSRI therapy, recent revised SSRI therapy, or anticipate need for revised or new SSRI therapy per health care provider

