PROMIS prescription pain medication mis-use scale - A participant completed survey of prescription medication misuse over the past 30 days. The survey is comprised of 7 questions on a 5-point ordinal scale of never/rarely/sometimes/frequently/almost always or not at all/a little bit/somewhat/quite a bit/very much[33]. This survey will be administered at baseline, 3 months, and 6 months post return of results.

PROMIS emotional distress depression 8b survey - A participant completed eight question survey assessing frequency of depression symptoms over the past 7 days[36]. This survey will be administered at baseline, 1 month, 3 months, and 6 months post return of results to the adult participants.

Opioid side effects – A participant completed survey of common opioid side effects experienced and the extent to which those side effects bothered the participant. This survey will be administered at baseline, 3 months, and 6 months post return of results to the adult participants.

Depression:

PROMIS emotional distress depression 8b survey - A participant completed eight question survey assessing frequency of depression symptoms over the past 7 days[36]. This survey will be administered at baseline, 1 month, 3 months, and 6 months post return of results to the adult participants.

PROMIS Pediatric Depressive Symptoms Short Form 8a- A pediatric (ages 8-17 years) participant completed eight question survey assessing frequency of depression symptoms over the past 7 days[37]. This survey will be administered at baseline, 3 months, and 6 months post return of results to the pediatric study participants .

Patient Health Questionnaire-8 – An 8 item survey completed by the participant assessing depression symptoms over the last two weeks. This survey will be administered at baseline, 3 months, and 6 months post return of results[38].

Antidepressant side effects – A participant completed survey of relevant antidepressant side effects. This survey will be administered at baseline, 1 month, 3 months, and 6 months post return of results.

Voils Medication Adherence - A participant completed three question survey, 5-point scale survey assessing participant medication adherence[39]. This survey will be administered to depression trial participants at baseline, 1 month, 3-months and 6 months post return of results.

All of the PROMIS® surveys can be found online[40].

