The effect of genotype guided antidepressants therapy on the secondary endpoint depression remission and achieving 5% reduction in PHQ-8 scores will be assessed by comparing the Intervention group subset with CYP2D6 UM or PM or CYP2C19 UM, RM, or PM phenotypes the

Control group subset with CYP2D6 UM or PM or CYP2C19UM, RM, or PM phenotypes using a test of two-proportions with an alpha of 0.05. The effect of genotype guided antidepressants therapy on the secondary endpoints, medication adherence, PHQ-8 scores, and medication side effect severity burden, will be assessed by comparing the Intervention group subset with CYP2D6 UM or PM or CYP2C19 UM, RM, or PM phenotypes the Control group subset with CYP2D6 UM or PM or CYP2C19 UM, RM, or PM phenotypes using a two-sided Mann Whitney test with an alpha of 0.05. Participants that do not have metabolizer phenotypes will not be included in these analyses.

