11.2 Data Element Definitions

Clinically significant pain reduction: Whether or not the pain reduction score is ≤ 0.7 . If the pain reduction score is ≤ 0.7 , clinically significant pain reduction is achieved, if pain reduction scores is > 0.7 , clinically significant pain reduction is not achieved.

Depression symptom control: The change in the PROMIS Emotional Distress - Depression 8b or PROIMIS pediatric Depression 8a survey depression score from baseline to time t.

Depression remission: A. Whether or not the summed raw PROMIS emotional distress depression 8b survey responses are ≤ 16 , which is equivalent to the participant responding “rarely” or “never” to most or all of the PROMIS emotional distress - depression 8b survey questions. B. Whether or not the PHQ-8 scores are ≤ 4 , which is equivalent to depression severity being none-mild.

Depression (PHQ-8) score: The sum of the responses to the PHQ-8 survey, range from 0 to 24.

Depression (T) score: The T-score converted summed responses to the PROMIS emotional distress depression 8b survey. The T-score conversion is centered around 50 with standard deviation of 10.

Depression severity: The depression score converted to depression severity (none, mild, moderate, severe) based on the scoring guide for the PROMIS emotional distress depression 8b survey.

Medication adherence: The scored responses to the Voils Medication Adherence survey.

Medication concordance: Whether or not the medication the participant is prescribed after the intervention is concordant with the participants CYP2D6 and, for the depression trial, CYP2C19 phenotype.

Medication side effects severity burden: (Depression only) The sum of the scored severity (none = 0, mild = 1, moderate = 2, severe = 3) for common SSRI side effects.

Opioid misuse score: The T-score converted summed responses to the PROMIS prescription medication misuse 7a survey. The T-score conversion is centered around 50 with standard deviation of 10.

Opioid persistence: Defined as ≥ 1 opioid prescription refill between 90 days and 180 days after the surgical procedure.

Opioid usage: The average daily morphine equivalents in mg (MED) in past 7 days. MEDs will be calculated using data from the opioid usage survey.

Overall well-being: Defined as the T-score converted summed responses to the PROMIS 43/PROMIS 37 pediatrics survey. The T-score conversion is centered around 50 with standard deviation of 10.

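### Depression remission is scored on 6-month status alone, with no baseline condition and no entry score; 50% PHQ-8 response breaks down at low baselines, and PROMIS remission has no definition for ages 8-17

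*Combined protocol and SAP*

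**What the plan says.** - **Remission.** Section 3.2 gives two versions, "Achieve remission at 6 months, defined as PROMIS depression score ≤ 16" and "Achieve remission at 6 months, defined as PHQ-8 score ≤ 4". Section 11.2 makes the PROMIS version specific: "Whether or not the summed raw PROMIS emotional distress depression 8b survey responses are ≤ 16". None of these refers to baseline.
- **Response.** Section 3.2 has "Achieve 50% reduction in PHQ-8 scores at 3 months, relative to baseline", with no minimum baseline. Section 11.2 gives the PHQ-8 range as 0 to 24. Section 10.5 instead speaks of "achieving 5% reduction in PHQ-8 scores".
- **Entry.** Section 5.1 requires documented or provider-reported depression, "Evidence of depressive symptoms for at least 3 months based on patient interview or documentation in electronic health records", and a recent or anticipated SSRI start or revision. No PHQ-8 or PROMIS threshold appears in Section 5.1 or 5.2. The chronic pain criterion asks for pain over the last 3 months; the depression criterion does not require the 3 months to be the most recent.
- **Analysis.** Section 10.5 compares remission and response by a test of two proportions at 0.05, restricted by metabolizer phenotype only, with no baseline adjustment.
- **Forms.** Section 7.3 gives the 8b form to adults ("This survey will be administered at baseline, 1 month, 3 months, and 6 months post return of results to the adult participants") and the Pediatric Short Form 8a to ages 8-17. The PHQ-8 has no age split. Section 10.4 plans a pediatric-to-adult crosswalk for T-scores in the primary analysis.

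**The concern.** An endpoint worded as achieving remission suggests a move from symptomatic to not symptomatic. As defined, it is a state at 6 months. Entry admits people who have recently started or changed an SSRI, and some may already be below the cut-off at baseline. If they stay there, they are counted as successes in both arms. The reported rate then cannot be read as recovery, and if treatment does little for this group, the difference between arms shrinks.

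The 50% response has a different fault: at very low baselines the percentage is either undefined or met by a trivial change.

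The third gap concerns children. They are eligible from age 8 and pediatric/adult is a randomisation stratum (Section 4.1), yet one remission endpoint rests on a form they do not complete.

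**Working it through.** **1. Sample size used for the illustration.** Section 10.1 gives 271 per arm for effect size 0.28, two-sided alpha 0.049 and 90% power. A two-sample t-test calculation gives 270.4, so 271 per arm and 542 in total, with power 90.1%. The plan's figure reproduces. It is for the primary endpoint and is borrowed here only as n per arm. No power is stated for remission or response.

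**2. What the remission rule counts.** Baseline PHQ-8 3 and 6-month PHQ-8 3 satisfies 4 or below at 6 months, so it is a remission. This follows from the definition and needs no assumption.

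**3. Possible dilution.** The documents give no baseline share below the cut-off, no remission rates and no rate of staying in remission, so every input here except n is assumed. Let q be the share at or below the cut-off at baseline, p the remission rate among the rest, and r the share of baseline remitters still below at 6 months. The all-participant rate in an arm is (1 − q)p + qr. Take p = 30% control and 40% intervention, 271 per arm, two-sided alpha 0.05. With q = 0, power is 69%; that is the reference.

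For q = 20% and r = 85% in both arms:
- Control: 0.8 × 0.30 + 0.2 × 0.85 = 0.41
- Intervention: 0.8 × 0.40 + 0.2 × 0.85 = 0.49
- Share of control remissions already below the cut-off at entry: 0.17 / 0.41 = 41%

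For q = 20% and r = 75% control, 85% intervention:
- Control: 0.24 + 0.15 = 0.39
- Intervention: 0.32 + 0.17 = 0.49

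The restricted analysis has 271(1 − q) per arm (217 at q = 20%) and compares 30% with 40%.

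| q | All participants, r = 85% in both arms | All participants, r = 75% v 85% | Restricted |
|---|---|---|---|
| 10% | 57% | 66% | 64% |
| 20% | 46% | 65% | 59% |
| 30% | 37% | 64% | 53% |

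Restriction gains 7, 12 and 16 points in the first case (from unrounded values) and loses power in the second. The direction depends on whether treatment affects staying in remission.

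**4. 50% PHQ-8 response.** Percentage fall = (baseline − follow-up) / baseline. At baseline 0 this is 0/0 or a negative number over 0, so undefined. At baseline 1 the smallest qualifying fall is 1 point (100%), and at baseline 2 it is also 1 point (50%). At baseline 4 it is 2 points. The dilution arithmetic in step 3 does not apply to this endpoint.

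**5. Ages 8-17.** Section 11.2 defines PROMIS remission on the 8b raw sum, and Section 7.3 gives these participants the 8a form. The same section's entry for depression symptom control names both forms; the remission entry names only 8b. The crosswalk in Section 10.4 is stated for T-scores, not for a raw cut-off of 16. These participants therefore have no observed PROMIS remission value. They do have PHQ-8 remission.

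**6. Timing of the baseline score.** Section 7.2 collects depression baseline data following consent. Section 4.1 randomises after consent, and Section 7.4 once the DNA sample is collected, possibly by mailed kit. No section places the baseline survey before randomisation.

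**The case against.** The strongest reply is that being in remission at 6 months, in everyone with an actionable phenotype, is a legitimate pragmatic outcome. A participant who starts low after a recent SSRI change may stay low or relapse, and genotype-guided selection could affect which. That stands. A reader might infer that these events cannot reflect treatment, or that restricting must gain power; the documents support neither, and step 3 shows the result can go either way.

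A second reply is that restricting on baseline is safe only if baseline precedes allocation. A reader might assume that it does, but no section says so, and the trial is open label with self-reported scores. This also stands and shapes the fix.

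Third, the objectives describe participants who need new or revised therapy, which may mean few start below the cut-off. That is possible, but entry does not enforce it.

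Fourth, these are secondary endpoints to be read conservatively without multiplicity adjustment (Section 10.9), the changes in PROMIS and PHQ-8 already use baseline, and a separate detailed SAP is promised (Section 10.2). This limits the weight of the point. It does not supply the missing rules in Sections 10.5 and 11.2.

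Finally, a reader might infer that Section 10.8 would impute the missing 8b sums for children. Its wording is broad, but it does not address a form that was never administered and leaves details to the SAP.

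**Conclusion.** The point holds as one about definitions. Remission counts participants who were already below the cut-off and have not changed, 50% response has no rule for baseline 0 and accepts a 1-point fall at baseline 1 or 2, and PROMIS remission is undefined for ages 8-17. These statements rest on the text alone.

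The consequence for remission is a misleading label and possible dilution. A reader might infer a biased comparison or a raised false-positive rate. The documents do not support that, because the same rule applies to both randomised arms. The size is unknown: the 10-30% baseline share and all rates in the illustration are assumptions. Any power gain from restriction is conditional on little treatment effect on staying in remission. A reader might also extend the power loss to the response endpoint, but nothing calculated here shows that.

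**What to change.** In Sections 10.5 and 11.2:

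1. Report remission among actionable participants above the same cut-off at baseline (PROMIS 8b raw above 16; PHQ-8 above 4), using a score confirmed to precede randomisation. Beside it, report the all-participant 6-month proportion, labelled as in remission at 6 months. State in advance which is the main result.
2. Assess 50% PHQ-8 response among those with a pre-randomisation PHQ-8 above 4, which also removes the undefined case.
3. For ages 8-17, define PROMIS remission on the crosswalked adult T-score that corresponds to 8b raw 16, rather than leaving it missing or imputed.
4. Reconcile the 5% reduction in Section 10.5 with the 50% in Section 3.2 and the synopsis.

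The cost is wording and a check of survey dates against randomisation dates. Baseline PHQ-8 and PROMIS are already collected, and the crosswalk is already planned. The downside is smaller denominators in the restricted analyses. Any power gain quoted in support should be given as an assumption, not a result.

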4.1 Randomization

After participants provide informed consent/assent, participants will be randomized in a 1:1 allocation to the Intervention (i.e. immediate PGx testing and genotype-guided opioid or SSRI therapy with clinical decision support) and Control (i.e. usual care with delayed PGx testing) arms. Randomization will be stratified by trial and site or clinic with a random block size within each site or clinic. We anticipate variability in patient populations between recruiting sites or clinics and aim to balance the intervention assignments within the site or clinic unit. Additionally, the randomization for the chronic pain trial will be stratified by presence/absence of depression, and the randomization for the acute pain and depression trials will be stratified by pediatric/adult.

The randomization scheme will be generated by an unblinded statistician. Randomization assignments will be generated in real time in REDCap at the Coordinating Center.

4.2 Blinding

ADOPT PGx randomization assignments will not be blinded to the participants or their providers but will be masked to the UF call center personnel who may be administering some of the participants follow-up surveys. Due to the nature of the intervention, it is impossible to completely mask participants and providers from the pharmacogenetic testing and return of results, hence participants, providers, and local study personnel will not be blinded. While the UF call center personnel administering follow-up surveys will be masked from the results and randomization, study-arm specific questions in the final (6 month) survey may reveal study arm randomization. Additionally, participants may volunteer to reveal their randomization or PGx testing results. If the randomization or phenotype is revealed to the call center, prior to administering the 6 month surveys, it will be documented in the database.

5. STUDY POPULATION

5.1 Inclusion Criteria

Acute Pain

- Age \geq 8 years
- English speaking or Spanish speaking
- Elective/planned surgery types with planned or anticipated to be treated with tramadol, hydrocodone, or codeine pain management at an enrolling site, which may include orthopedic surgeries(e.g. arthroplasty, spine, etc.), open abdominal surgery, or cardiothoracic surgery and others

Chronic Pain

- Age \geq 18 years
- English speaking or Spanish speaking
- Seen at primary care clinics at an enrolling site (such as, but not limited to, Internal Medicine, Family Medicine, Pediatrics) or seen in pain-relevant specialty clinics
- History of pain for at least the last 3 months
- Currently treated or being considered for treatment with tramadol, hydrocodone, or codeine to improve pain management

Depression

Age \geq 8 years

- English speaking or Spanish speaking
- Patients followed at psychiatry clinics or primary care clinics at an enrolling site (such as, but not limited to, Internal Medicine, Family Medicine, or Pediatrics)
- Documentation of depression and/or provider report of depression
- Evidence of depressive symptoms for at least 3 months based on patient interview or documentation in electronic health records
- Recent initiation of SSRI therapy, recent revised SSRI therapy, or anticipate need for revised or new SSRI therapy per health care provider

